11.7.7 Time to Headache Relief

The time to headache relief will be presented by treatment group using a Kaplan-Meier analysis. This summary will be presented for the ITT population, based on the first dose.

The number of subjects experiencing headache relief, and the number of subjects censored, will be summarized. The Kaplan-Meier estimates, and 95% confidence intervals calculated using the log-log transformation, of the number of hours for 25%, 50%, and 75% of subjects to experience headache relief will be presented. The Kaplan-Meier estimate, and 95% confidence interval, of the probability of experiencing headache relief will be presented at the 0.5, 1, 1.5, 2, 3, 4, and 24-hour post-dose time points.

Time to headache relief is calculated as:

{1} For subjects randomized with moderate or severe headache pain: time [pain is none or mild] minus time [dosing for moderate or severe pain] and {2} For subjects randomized with mild headache pain: time [pain is none] minus time [dosing for mild pain]

Subjects who do not report a headache with severity of mild or none, or who report a headache with a severity of mild or none after 24 hours post-dose will be censored at the time of their last non-missing post-dose headache severity assessment at or before 24 hours. Subjects with missing baseline headache severity, or who report a headache severity of none (0) at baseline, will be censored at the time of first dose.

A figure of the Kaplan-Meier analysis will also be presented.

11.7.8 Time to MBS-Free

The time to MBS-free will be presented by treatment group using a Kaplan-Meier analysis. This summary will be presented for the ITT population, based on the first dose.

The number of subjects experiencing MBS-free, and the number of subjects censored, will be summarized. The Kaplan-Meier estimates, and 95% confidence intervals calculated using the log-log transformation, of the number of hours for 25%, 50%, and 75% of subjects to experience MBS-free will be presented. The Kaplan-Meier estimate, and 95% confidence interval, of the probability of experiencing MBS-free will be presented at the 0.5, 1, 1.5, 2, 3, 4, and 24-hour post-dose time points.

Time to MBS-free will be calculated as:

date/time a lack of presence of the baseline MBS is reported –
date/time of first dosing

Subjects who do not record the absence of their baseline MBS, or who record such a response after 24 hours post-dose will be censored at the time of their last non-missing post-dose symptom assessment at or before 24 hours. Subjects with missing baseline MBS will be censored at the time of first dose. Subjects who report that no symptoms were present at baseline will be excluded from the analysis.

A figure of the Kaplan-Meier analysis will also be presented.

11.7.9 Disability

Counts and percentages of the level of disability will be presented at the 0.5, 1, 1.5, 2, 3, 4, 24, and 48-hour post-dose time points. This will be summarized based on the first dose using the ITT population, and based on the second dose for recurrence and rescue using the ITT-2nd Dose population.

Disability is measured on a four-point scale.

- Not at all (0)
- Mild interference (1)
- Marked interference (2)
- Completely, needs best rest (3)

Treatment comparisons between the lasmiditan groups and placebo will be tested using the

Cochran-Mantel-Haenszel test statistic using modified ridit scores, controlling for background use of medication to reduce the frequency of migraine episodes.

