### 5.6.3 Treatment

Subjects will be allowed up to 8 weeks to treat an acute migraine attack of moderate or severe intensity that is not improving. The attack is to be treated within 4 hours of onset.

- **Prior to dosing the subject will record:**
  - Time of onset
  - Time migraine pain becomes moderate or severe and the severity ((2) moderate or (3) severe) of the pain.
  - Presence or absence (yes or no) of each of the following associated symptoms of migraine: nausea, phonophobia and photophobia.
    - From the list of associated symptoms **present** the subject will identify which **ONE** is most bothersome to them as the MBS.
  - Presence or absence (yes or no) of vomiting.
  - Degree of interference with normal activities
- **Subject will dose with study drug and record time of dosing.**
- Subject will record their response to treatment for 48 hours after dosing with study drug. Total time to record response is up to 72 hours (See [Section 9.1.8](#)).
- Subjects will be asked about any adverse events (if they are feeling anything unusual) and about the use of any concomitant medications.

### 5.6.4 End of Study/Visit 2

The following assessments will be performed:

- Collect any unused study drug and review dosing compliance.
- Collect resource utilization (See [Section 9.1.1.3](#)).
- Collect information on missed days of work and/or school due to migraine.
- Have subject complete C-SSRS (See [Section 9.1.6](#) and [Appendix 5](#)).
- Review any information reported since **Visit 1** regarding AEs and use of concomitant medication and confirm/assess for AEs and use of concomitant medications not already reported.
- Perform a brief symptom-related physical examination if indicated by an AE (See [Section 9.1.2](#)).
- Obtain vital sign readings (See [Section 9.1.3](#)).
- Perform a 12-lead ECG (See [Section 9.1.4](#)).
- Collect blood and urine samples for clinical laboratory tests (hematology, chemistry, and urinalysis) (See [Section 9.1.5](#)). The laboratory tests will include a urine pregnancy test for WOCBP. A positive urine pregnancy test will be confirmed with a serum  $\beta$ HCG test. (The confirmatory test may be run in the local clinical laboratory).
- Subject's participation in study is complete.

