### 9.1.8 Subject Diary

Subjects will be trained on the use of the electronic diary at **Screening/Visit 1**. Efficacy data will be collected in an electronic diary for an attack. Subjects will record the date and time at which their migraine headache starts and when it first becomes moderate or severe. They will also record the date and time of taking the first dose of study drug.

Subjects will be asked to assess their headache severity at specified time points: 0 (pre dose), 0.5, 1, 1.5, 2, 3, 4 and 24 and 48 hours post dose using the IHS four point headache severity rating scale (0 = no pain, 1 = mild pain, 2 = moderate pain, and 3 = severe pain). The need for rescue medication and second dosing of study drug or an alternative treatment will be assessed between 2 and 24 hour and at 48 hours. Recurrence of pain and second dosing of study drug will be assessed between 2 and 24 hours and at 48 hours.

At the same time points, 0 (pre dose), 0.5, 1, 1.5, 2, 3, 4, 24 and 48 hours, subjects will grade the degree of interference with normal activities and the presence or absence (yes or no) of accompanying symptoms: photophobia, phonophobia and nausea. At time 0 (pre dose) subjects will select from the accompanying symptoms present (nausea, phonophobia or photophobia) which one is the most bothersome to them. Subjects will be asked to record the presence or absence (yes or no) of vomiting. Subjects will also be asked to record the exact time at which headache relief became meaningful to them and the time at which they become headache pain free. At 2 hours subjects will be asked to record their global impression of change using a 7-point scale (very much better, much better, a little better, no change, a little worse, much worse, and very much worse).

The diary will also be used to record any symptoms or side effects the subject is experiencing and the use of any concomitant medications from **Visit 1** through to **EoS/Visit 2**

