3.3 Exploratory Efficacy Endpoints

- Headache pain-free at 0.5, 1, 1.5, 3, 4, 24, and 48 hours post-dose based on first dose
- Sustained headache pain-free at 24 and 48 hours post-dose based on first dose
- MBS-free at 0.5, 1, 1.5, 3, 4, 24, and 48 hours post-dose based on first dose
- Presence of migraine symptoms (nausea, phonophobia, photophobia, vomiting) at all-time points based on first and second dose
- Headache relief at all time points based on first dose
- MBS-free at 0.5, 1, 1.5, 2, 3, 4, 24, and 48 hours post-dose by chosen MBS based on first dose
- Time to headache pain-free through 24 hours after first dose
- Time to headache relief through 24 hours after first dose
- Time to MBS-free through 24 hours after first dose, overall and separately for each symptom
- Disability at all time points based on elapsed times since first and second doses
- Incidence of rescue or recurrence medication use at 2 hours, between 2 and 24 hours, and between 24 and 48 hours post first dose
- Incidence of headache recurrence
- Patient global impression of change (PGIC) scale at two hours post-dose, based on elapsed times since first and second dose
- Headache pain-free after a second dose, separately for rescue and recurrence, at all time points
- Time to headache pain-free through 24 hours after a second dose, separately for rescue and recurrence

- Headache relief after a second dose, separately for rescue and recurrence, at all time points
- Time to headache relief through 24 hours after a second dose, separately for rescue and recurrence
- MBS-free after a second dose, separately for rescue and recurrence, at all time points, overall and separately for each symptom
- Time to MBS-free through 24 hours after a second dose, separately for rescue and recurrence, overall and separately for each symptom

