11 EFFICACY ANALYSES

This section details the specifications for summarizing efficacy endpoints.

The primary and key secondary efficacy analyses will be performed on the ITT, mITT, and PP populations. The primary analysis population is the mITT population. Exploratory efficacy analyses will be performed on the ITT and ITT-2nd Dose populations, depending on the endpoint. Efficacy responses will also be presented in a listing.

Unless otherwise stated, all primary, secondary, and exploratory efficacy hypotheses will be tested using a logistic regression model with treatment group and background use of medication to reduce the frequency of migraine episodes as covariates. For treatment comparisons, an estimate of the odds ratio of achieving a response, as well as the corresponding confidence interval and p-value using Wald's test, will be computed. Tests of the primary and key secondary endpoints will be conducted at a one-sided significance level of 0.025; tests of all other endpoints will be conducted at a two-sided significance level of 0.05.

Analyses of second-dose endpoints with too few subjects in the treatment-sequence-subpopulation groups may have too little data separation for a logistic regression model to reach a stable solution. For these models, the "Firth" modification of the maximum likelihood estimation will be used to achieve a solution.

The efficacy endpoints will depend on data collected by e-diary that depends on subject's response entry in the correct order and at the expected scheduled e-diary assessment times. Assessment times are analyzed as calculated by the e-diary and not as part of analysis programming.

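### The first-dose disability test leaves out the pre-dose disability grade the diary already collects, and may give up some power

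*SAP*

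**What the plan says.** Protocol 5.6.3 lists "Degree of interference with normal activities" among the items a subject records before taking study drug. Protocol 9.1.8 sets the full schedule: "0 (pre dose), 0.5, 1, 1.5, 2, 3, 4, 24 and 48 hours, subjects will grade the degree of interference with normal activities". SAP section 5 takes efficacy baselines from the diary's Hour-0 assessment.

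SAP 11.7.9 uses only the later grades: "Counts and percentages of the level of disability will be presented at the 0.5, 1, 1.5, 2, 3, 4, 24, and 48-hour post-dose" time points. The treatment comparison there is a "Cochran-Mantel-Haenszel test statistic using modified ridit scores, controlling for background use of medication to reduce the frequency of migraine episodes". Preventive use is the only stratification factor. The general efficacy model in SAP section 11 has no baseline score either; it takes "treatment group and background use of medication to reduce the frequency of migraine episodes as covariates". SAP 8.5, which lists characteristics of the treated attack, does not include pre-dose disability.

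SAP 3.3 classes the endpoint as exploratory: "Disability at all time points based on elapsed times since first and second doses". It is outside the testing sequence of SAP 11.1, and SAP section 11 states that "tests of all other endpoints will be conducted at a two-sided significance level of 0.05". Protocol 10.5.4.5 planned only summary statistics for disability; the test was added in the SAP (section 5.1).

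**The concern.** If post-dose disability depends on how disabled the subject was at dosing, that part of the variation stays in the error of a test stratified only by preventive use. A baseline value on the same scale is often a useful covariate, and here it costs no extra data collection.

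The other main outcomes already refer back to the pre-dose state. Pain-free and headache relief are defined from baseline severity, and MBS-free from the symptom chosen before dosing. The patient global impression uses the same test as disability (SAP 11.7.12), but it is itself a rating of change and has no pre-dose score to adjust for. Disability has one, and it goes unused. At stake is the power of an exploratory comparison.

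**Working it through.** **The plan's own power figure.** The documents give no power, effect size or correlation for disability. Their stated power is for 2-hour pain-free: above 90% for each dose with 570 per arm, one-sided 0.025. With a pooled variance under the null, power = Φ((d − 1.96·SE₀)/SE₁). For 7.4% versus 13.6%: d = 0.062, SE₀ = √(2 × 0.105 × 0.895/570) = 0.01816, SE₁ = √((0.074 × 0.926 + 0.136 × 0.864)/570) = 0.01807, so power = Φ(1.46) = 92.8%. The same formula gives 94.6% for 50 mg and 99.99% for 200 mg. The stated figure reproduces, and 570 per arm is carried forward.

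**Rough size by normal approximation.** Adjusting for a baseline with correlation r removes a fraction r² of the variance. Starting from 80% power at two-sided 0.05, adjusted power = Φ((1.960 + 0.842)/√(1 − r²) − 1.960):
- r = 0.2: 81.6%
- r = 0.3: 83.6%
- r = 0.4: 86.4%
- r = 0.5: 89.9%
- r = 0.6: 93.8%

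**Simulation of the actual test.** Within stratum k, each subject's score is a = midrank/(n_k + 1). The statistic is Z = Σ_k[Σ_active a − n₁ₖ·ā_k] / √(Σ_k [n₁ₖn₀ₖ/(n_k(n_k − 1))]·Σ(a − ā_k)²), rejecting when |Z| > 1.96. The planned strata are preventive use; the alternative strata are preventive use × pre-dose grade. All sets use 570 per arm, four-level grades cut from correlated normal variables, and assumed category proportions.
- Set A: 1,500 runs.
- Set B: 2,500 runs; pre-dose levels 5/30/45/20%, placebo post-dose levels 20/35/30/15%, 20% on preventives, effect chosen for about 80% power under the planned test.
- Set C: 2,500 runs; 20% on preventives, 3% of pre-dose grades missing and placed in their own stratum.

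Power in percent, planned → stratified:

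| Assumed r | Set A | Set B | Set C | Gain (points) |
|---|---|---|---|---|
| 0 | not run | 80.6 → 80.4 | 77.1 → 76.4 | −0.2, −0.7 |
| 0.2 | not run | 81.3 → 81.8 | 76.4 → 77.1 | 0.5, 0.7 |
| 0.3 | 74 → 76 | 80.3 → 83.0 | 77.8 → 79.2 | 2, 2.7, 1.4 |
| 0.4 | 72 → 77 | 80.9 → 85.7 | 76.6 → 81.8 | 5, 4.8, 5.2 |
| 0.5 | 74 → 80 | 80.4 → 88.1 | 75.1 → 83.2 | 6, 7.7, 8.1 |
| 0.6 | 75 → 86 | 81.1 → 91.7 | 77.4 → 87.6 | 11, 10.6, 10.2 |

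The planned test's power should not depend on r; its drift down the columns is simulation error. The standard error of one estimate is √(0.74 × 0.26/1500) = 1.1 points in set A and √(0.8 × 0.2/2500) = 0.8 points in set B. Cutting the scores into four grades weakens the correlation (r = 0.5 becomes a Spearman correlation of 0.43 in set B), which is why the simulated gains fall below the approximation.

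With no treatment effect, rejection rates were 4.2–5.3% in set B and 4.4–5.5% in set C across both tests.

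**The case against.** The strongest reply is that nothing here is an error. The SAP adjusts its efficacy models for the randomisation stratum only, the primary endpoint included, and adding a baseline to one exploratory scale is a preference. That stands as far as validity goes. It does not remove the efficiency argument, because the pre-dose grade is already collected.

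A second reply is that the dependence on the starting grade is assumed. That also stands: no document supports calling it strong, and below about r = 0.2 the gain is negligible.

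Three stronger readings are tempting, and the documents do not support them.

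- **Chance imbalance makes the planned test unreliable.** With no treatment effect, among the fifth of simulated trials with the largest pre-dose imbalance, the planned test rejected 8.5% of the time at r = 0.4 and 10.0% at r = 0.6, against 5.1% and 3.5% for the stratified test. The remaining trials offset this: if the overall rate is 5%, the other four fifths average (5 − 0.2 × 8.5)/0.8 = 4.1% at r = 0.4. Randomisation already allows for chance imbalance, and the overall error rate is not inflated.

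- **The same change should be made for the second dose.** Protocol 9.1.8.1 and 9.1.8.2 list what is recorded at a second dose, and a disability grade is not among the items. Such a grade would also come after randomisation and could be affected by the first dose, so conditioning on it changes the question. SAP section 11 already expects some second-dose groups to be small. Five grade levels (with missing) × 2 gives up to 10 strata, and any stratum holding only one arm drops out. In simulations with assumed groups of 14 and 12 (3,000 runs), stratifying cut power from 66% to 55% at r = 0 and from 68% to 61% at r = 0.4. With 30 and 25, it cut power from 74% to 68% at r = 0 and changed nothing at r = 0.4.

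- **The gain applies equally at every time point.** The simulations describe 2 hours with 570 per arm. First-dose data stop at the second dose (SAP 5.2) and missing grades stay missing (SAP 5.3), so the 24- and 48-hour tests have fewer subjects and the gain there may be smaller.

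**Conclusion.** The point holds for the first-dose disability comparisons, as an efficiency gain of low severity. The planned test is valid but does not use a baseline grade already collected. The gain ranges from nothing measurable to about 10–11 points of power as the assumed correlation runs from 0 to 0.6. At 570 per arm the downside is within simulation error, even when the pre-dose grade carries no information. These figures rest on an assumed correlation, assumed category distributions and a latent-normal model, none of which the documents supply. Disability is exploratory and outside the gatekeeping sequence, so no confirmatory conclusion changes.

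**What to change.** In SAP 11.7.9, state that the first-dose disability comparisons use the modified-ridit test stratified by pre-dose disability grade (four levels plus one for missing) crossed with preventive use. State also that the second-dose comparisons keep preventive use as the only stratification factor. Specify this before unblinding, since a covariate chosen after seeing results by arm would not be credible.

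The cost is a short addition to the text and one more variable in the TABLES statement. No new data are needed, the test remains a Cochran-Mantel-Haenszel test, and no proportional-odds assumption is added.

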11.7.10 Incidence of Rescue or Recurrence Medication Use

The count and percentages of subjects who take rescue or recurrence medication will be presented by treatment group and time point. The summary will be based on first dose using the ITT population.

The summary of study rescue or recurrence medication use will use the following three time points as applicable:

- At 2-hours post first dose
- Greater than 2, but less than or equal to 24 hours post first dose
- Greater than 24, but less than or equal to 48 hours post first dose

The combined summary of all rescue or recurrence medication use will use the following three time points as applicable:

- Less than or equal to 2 hours post first dose
- Less than or equal to 24 hours post first dose
- Less than or equal to 48 hours post first dose

A subject is defined to have used rescue medication within the specified time point if the subject takes a second dose of study drug within the time point or answers “Yes” to the e-diary question asking if any other medications have been used since the start of the migraine, and the medication is not considered a recurrence medication.

A subject is defined to have used recurrence medication if he or she records a mild (1), moderate (2), or severe (3) headache at baseline which becomes pain-free at 2 hours after the first dose, becomes more severe up to 48 hours after the first dose, and the subject takes a second dose of study drug within the time point or answers “Yes” to the e-diary question asking if any other medications have been used since the start of the migraine.

If the subject becomes pain-free at 2 hours after the first dose and records the use of rescue medication, but no headache severity is recorded between 2 hours after the first dose and the time of administration of a second dose, it will be assumed that the medication is taken for recurrence.

11.7.11 Incidence of Headache Recurrence

The counts and percentages of subjects who experience headache recurrence will be presented by treatment group. The summary will be based on first dose using the ITT population.

A subject is defined to have experienced headache recurrence if they record a mild (1), moderate (2), or severe (3) headache at baseline which becomes pain-free at 2 hours post first dose and then becomes more severe up to 48 hours post first dose.

If the subject becomes pain-free at 2 hours post first dose and records the use of rescue medication, but no headache severity is recorded, it will be assumed that the medication is taken for recurrence, and the subject will be counted as having experienced headache recurrence.

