##### **10.5.4.2 Headache recurrence**

The proportion of subjects with headache recurrence (moderate or severe headache at baseline, which became pain free at 2 hours post-dose and worsened again up to 48 hours post-dose) will be evaluated based on first dose. The frequency of recurrence will be compared by the same logistic regression model used for the primary endpoint analysis. The significance level of this exploratory analysis will be a nominal one-sided 0.05.

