5 GENERAL SPECIFICATIONS

This section details the specifications for summarizing all efficacy and safety endpoints.

Continuous variables will be summarized using descriptive statistics, i.e. n (number of subjects with available data), mean, median, standard deviation, minimum, and maximum. For those measures that are analyzed using change from baseline scores, descriptive statistics will also be presented on observed scores, unless otherwise noted.

Minimum and maximum values will be presented to the same precision as the raw data. Mean and median will be presented to one more decimal place than the raw data. Standard deviation will be

presented to two more decimal places than the raw data. P-values will be presented to three decimal places.

Categorical variables will be summarized using counts and percentages. Unless otherwise specified, percentages will be calculated using the numbers of subjects in the summarized population in each treatment group as denominators. Percentages will be presented with a precision of 1 digit after the decimal.

In this study, subject will enter the efficacy data on dosing and post-dose assessments in an e-diary. The e-diary records the date and time of the first dose and of the second dose and is programmed to assess specific time points and assessments as defined in the protocol based on the timing of the dose as recorded. This data is collected in the e-diary when e-diary is in migraine mode. Specifics of Migraine Mode are as below:

- Migraine Mode – First Dose
 - The e-diary enters Migraine Mode **ONLY** if the subject indicates taking his/her first dose of study medication
 - Post Dose Assessments will be completed using the Migraine Questions button at specific time intervals for up to 48 hours after the subject confirms taking study medication

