11.7.2 Sustained Headache Pain-Free

Sustained pain-free response will also be summarized at the 24 and 48-hour post-dose time points. This summary will be presented by treatment group for the ITT population, based on first dose.

Sustained Pain-Free is defined as experiencing headache pain-free at two hours after first dose and at the subsequent indicated assessment time, having not used any medications after the first dose.

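### Headache recurrence is set up as a percentage of all ITT subjects although only 2-hour pain-free subjects can recur, so a more effective arm will tend to look worse on this exploratory endpoint

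*SAP*

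**What the plan says.** **Definition and population.** Under SAP 11.7.11 a recurrence needs head pain at baseline "which becomes pain-free at 2 hours post first dose and then becomes more severe up to 48 hours post first dose". The same section adds: "The summary will be based on first dose using the ITT population". It gives no denominator. SAP 5 supplies the default: unless something else is specified, "percentages will be calculated using the numbers of subjects in the summarized population in each treatment group as denominators".

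**Test.** SAP 11.7.11 asks only for counts and percentages. Protocol 10.5.4.2 does ask for a comparison: "The frequency of recurrence will be compared by the same logistic regression model used for the primary endpoint analysis", and "The significance level of this exploratory analysis will be a nominal one-sided 0.05". SAP 11 says that, unless stated otherwise, "all primary, secondary, and exploratory efficacy hypotheses will be tested using a logistic regression model", and that "tests of all other endpoints will be conducted at a two-sided significance level of 0.05". SAP 5.1, which lists departures from the protocol, neither withdraws the recurrence comparison nor mentions the change of level.

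**Sustained pain-free.** SAP 11.7.2 reads: "Sustained Pain-Free is defined as experiencing headache pain-free at two hours after first dose and at the subsequent indicated assessment time". It also requires that no medication was used after the first dose. The endpoint is presented by arm in the ITT population at 24 and 48 hours.

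**The concern.** A subject who still has pain at 2 hours cannot be a recurrence case but sits in the denominator. The ITT percentage therefore combines two things: how many subjects became pain-free, and how many of those relapsed. The first is the primary endpoint, which the trial is powered to move. An arm with more 2-hour responders has more subjects who can relapse, so its percentage rises even if relapse per responder is identical. A reader of the table, or of an odds ratio from it, could take early efficacy for poor durability.

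The durability endpoint that should settle this has a gap. Pain is rated at 3, 4, 24 and 48 hours (protocol 9.1.8), but SAP 11.7.2 looks only at 2 hours and at one later time. A subject with pain at 3 or 4 hours who takes nothing and is pain-free at 24 hours is a recurrence under 11.7.11 and also sustained pain-free under 11.7.2. The same holds for pain at 24 hours that has gone by 48 hours, for the 48-hour endpoint.

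**Working it through.** **Inputs from the documents** (SAP 2.2, protocol 10.1): 2-hour pain-free rates of 7.4% (placebo), 18.8% (200 mg), 13.6% (100 mg) and 13.9% (50 mg); 570 per arm by first dose. **Assumed:** recurrence per 2-hour responder, r. The documents give no value; I use 30% and show 20% to 50%. I also take 570 as the ITT size per arm.

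**1. The plan's own figure.** The documents claim more than 90% power for pain-free at one-sided 0.025. A two-proportion test with pooled variance and no continuity correction gives 99.99% (200 mg), 92.8% (100 mg) and 94.6% (50 mg). The claim reproduces. The documents give no figure for recurrence.

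**2. Expected ITT recurrence with equal r = 0.30.** ITT rate = pain-free rate × r.
- Placebo: 0.074 × 0.30 = 2.22%, or 12.7 of 570.
- 200 mg: 0.188 × 0.30 = 5.64%, or 32.1 of 570.
- 100 mg: 0.136 × 0.30 = 4.08%; 50 mg: 0.139 × 0.30 = 4.17%.

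Odds ratio for 200 mg = (0.0564/0.9436) / (0.0222/0.9778) = 2.63. For 100 mg it is 1.87 and for 50 mg 1.92.

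**3. Chance of nominally significant apparent harm.** Unadjusted Wald test of the log odds ratio, 200 mg, r = 0.30:
- log OR = 0.968
- SE = √(1/12.7 + 1/557.3 + 1/32.1 + 1/537.9) = 0.337
- z = 2.87
- Power at two-sided 0.05 = Φ(2.87 − 1.96) = 82%

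| Assumed r | 200 mg | 100 mg | 50 mg |
|---|---|---|---|
| 20% | 64% | 30% | 32% |
| 30% | 82% | 43% | 45% |
| 40% | 92% | 54% | 57% |
| 50% | 96% | 64% | 67% |

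A pooled-variance test and a simulation of 100,000 trials per setting both give 85% for 200 mg at r = 0.30.

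**4. When the direction reverses.** The ITT percentages are equal when (recurrence per responder on active) / (that on placebo) = 7.4% / active pain-free rate:
- 200 mg: 7.4/18.8 = 0.39
- 100 mg: 7.4/13.6 = 0.54
- 50 mg: 7.4/13.9 = 0.53

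Below these ratios the active arm looks better. Above them a real durability benefit is hidden: in the simulation, if 200 mg cuts recurrence per responder by a quarter, its ITT percentage is still the higher one in 93% to 99% of trials for placebo r of 20% to 50%. If it halves it, in 66% to 78%.

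**5. With responders as denominator.** Expected denominators are 570 × 0.074 = 42, 570 × 0.188 = 107, 570 × 0.136 = 78 and 570 × 0.139 = 79. Equal r then gives equal percentages. In the simulation at r = 0.30, lasmiditan is significantly worse in about 2% of trials at every dose, close to the 2.5% nominal for one direction.

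**The case against.** **The endpoint is exploratory.** It is listed as such in SAP 3.3 and stands outside the testing sequence in SAP 11.1. This stands: no confirmatory claim is touched.

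**The test is not firmly specified.** SAP 11.7.11 names none, whereas 11.7.9 and 11.7.12 do. Protocol 10.5.4.2 sets a one-sided 0.05 level without a direction. If that side is benefit, the protocol's test cannot declare harm. If it is harm, the chance for 200 mg at r = 0.30 is Φ(2.87 − 1.645) = 89%. So the 82% belongs to the SAP's two-sided default, and the conflict of levels is part of the point. A comparison is nevertheless called for in both documents, and the misleading percentages appear whether or not anyone tests them.

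**The denominator is inferred.** True, but the inference is firm. Where the SAP wants a narrower denominator it says so, as in 11.7.1, 11.7.5 and 11.7.8.

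**The ITT denominator keeps the randomised comparison; responders are a post-randomisation subset.** This stands, and it is why the responder rate should be descriptive. It is also imprecise: with 42 placebo responders and r = 30%, the 95% half-width is 1.96 × √(0.3 × 0.7/42) = about 14 percentage points.

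**Much of the remedy is already planned.** Sustained pain-free is already presented by arm in ITT subjects. That also stands; only the gap in its definition needs closing.

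A reader might go further and infer that lasmiditan is bound to look worse, or that the sustained pain-free and recurrence tables contradict each other. The documents support neither. The first depends on a recurrence rate per responder that they do not give. On the second, any medication after the first dose disqualifies a subject from sustained pain-free, so the overlap is confined to unmedicated pain that has gone by the later assessment. A subject pain-free at 2 and 24 hours with pain at 48 hours is sustained at 24 hours and recurrent by 48 hours with no inconsistency.

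**Conclusion.** The point holds for an exploratory endpoint. Followed as written, the plan yields a recurrence comparison confounded by the 2-hour response. Other things equal, the more effective arm will tend to look worse, most of all at 200 mg: about 2.2% v 5.6% under equal recurrence of 30% per responder. The sizes rest on the planning pain-free rates, 570 ITT subjects per arm and an assumed recurrence rate; the reversal ratios rest on the pain-free rates alone. The protocol and SAP also disagree on the significance level, without explanation. The overlap between sustained pain-free and recurrence is real but limited, and the documents do not allow its size to be estimated. Nothing here bears on the primary or key secondary results.

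**What to change.** - **SAP 11.7.11 and protocol 10.5.4.2:** present recurrence descriptively as n/N among subjects pain-free at 2 hours, with the ITT count beside it. Label the responder percentage as a non-randomised comparison and note the small placebo denominator.
- **Drop the logistic test with the ITT denominator.** This also removes the conflict between one-sided and two-sided 0.05. List the change in SAP 5.1; protocol 10 allows analysis changes that do not alter a principal feature to be made in the SAP without an amendment.
- **Durability:** keep the planned ITT analysis of sustained pain-free as the between-arm comparison, and add to the definition in SAP 11.7.2: *and no recorded headache pain at any assessment between 2 hours and that time point*.

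The cost is a few lines of text and some table programming. The diary already collects the data. Recurrence becomes a less precise, descriptive rate, and sustained pain-free rates may fall a little.
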